## **6.6 Emergency breaking of assigned treatment code**

Emergency unblinding should only be undertaken when it is essential to treat the subject safely and efficaciously. Most often, study treatment discontinuation and knowledge of the possible treatment assignments are sufficient to treat a study subject who presents with an emergency condition. A complete set of emergency code break cards will be provided to the investigator site(s) and a complete set will be available at Novartis. All code break cards must be retained until the end of the study and returned to Novartis. They must be stored in a secure place but be accessible in case of emergency. The investigator will receive a blinded code break card for each subject, with the details of drug treatment covered by a removable, scratch-off cover. In an emergency, the scratch-off cover can be removed to determine the treatment. The scratch-off covers are not to be removed for any reason other than an emergency. When the investigator removes the scratch-off cover he/she must note the date, time, and reason for removing it and retain this information with the case report form documentation. The unblinded treatment code should not be recorded on the CRF. The investigator must also immediately inform the Novartis local monitor that the code has been broken.

It is the investigator's responsibility to ensure that there is a procedure in place to allow access to the code break cards in case of emergency. If appropriate, the investigator will inform the subject how to contact his/her backup in cases of emergency when he/she is unavailable.

An assessment will be done by the appropriate site personnel and the sponsor after an emergency unblinding to assess whether or not study drug should be discontinued for a given patient and, if applicable, whether the patient can continue. Patients who undergo emergency unblinding and are discontinued cannot be re-enrolled in the study.

## **6.7 Treatment exposure and compliance**

Patients will receive all study medication at the Investigator site. Study medication will be administered by site personnel, compliance will be ensured by appropriate training of site personnel. The date and time of administration of study drug will be recorded in the dosage administration record section of the eCRF.

Pharmacokinetic parameters (i.e., measures of treatment exposure) will be determined in all subjects treated with CLR325.

## **6.8 Recommended treatment of adverse events**

At present there is insufficient information to provide specific recommendations regarding treatment of adverse events. Medication used to treat AEs must be recorded on the Concomitant medications/Significant non-drug therapies section of the source documentation.

Medication used to treat AEs must be recorded on the Concomitant medications/Significant non-drug therapies CRF.

## **6.9 Rescue medication**

Rescue medications are not applicable given that all patients in this study will have stable disease.

## **6.10 Concomitant treatment**

All prescription medications, over-the-counter drugs and significant non-drug therapies (including physical therapy and blood transfusions) administered or taken within the timeframe defined in the entry criteria prior to the start of the study and during the study, must be recorded on the Concomitant medications/ Significant non-drug therapies section of the (e)CRF. Medication entries should be specific to trade name, the single dose and unit, the frequency and route of administration, the start and discontinuation date and the reason for therapy.

While it is preferred that changes in prescription medications should not be made during the treatment period, changes in patient's baseline medications are allowed if deemed necessary by the investigator.

# **7 Discontinuation and study completion**

## **7.1 Discontinuation of study treatment**

Patients may voluntarily discontinue study treatment for any reason at any time.

The investigator must discontinue study treatment for a given patient if, on balance, he/she believes that continuation would be detrimental to the patient's well-being.

Study treatment must be discontinued under any of the following circumstances:

- Patient withdraws consent
- Any protocol deviation that results in a significant risk to the subject's safety
- Emergence of the following adverse events:
  - Acute myocardial infarction
  - Worsening myocardial ischemia
  - Sustained atrial or ventricular tachycardia
  - AICD discharge or anti-tachycardia pacing by the AICD in a patient with an AICD in place
  - An increase in non-sustained ventricular tachycardia or ventricular ectopy deemed clinically concerning by the investigator
  - Severe allergic reaction (e.g., angioedema)
- Occurrence of persistent elevation of systolic blood pressure to >180 mmHg or diastolic blood pressure >100 mm Hg
- Occurrence of symptomatic hypotension requiring persistent medical intervention (i.e. fluid replacement or inotropic therapy). Note that change of patient position does not qualify as an intervention if the need for this change in position is not persistent
- A drop in cardiac index of > 30% as compared to the average of all cardiac index measurements obtained prior to the start of infusion. All cardiac index values showing a 30% drop from baseline should be repeated and study drug terminated only if values are confirmed.
- Any clinically significant cardiac arrhythmia resulting in hemodynamic instability or requiring medical intervention to terminate
- Any of the following laboratory abnormalities:
  - Elevation in white blood cell count to greater than 2.5x above the ULN
  - Elevated AST or ALT > 8x above the ULN
  - Elevated AST or ALT > 3x above the ULN and TBL > 2x the ULN but without an increase in ALP to >2x the ULN
  - Elevated AST or ALT > 3x above the ULN and symptoms of malaise, fatigue, abdominal pain, nausea, vomiting, or rash with eosinophilia.

The appropriate personnel from the site and Novartis will assess whether study treatment should be discontinued for any patient whose treatment code has been broken inadvertently for any reason.

Patients who discontinue study treatment or who decide they do not wish to participate in the study further should NOT be considered withdrawn from the study UNLESS they withdraw their consent (see protocol [Section 7.3](#)). They should return to the clinic as soon as possible for the end of study visit assessments indicated in the [Assessment Schedule](#). If they fail to return for these assessments for unknown reasons, every effort (e.g. telephone, e-mail, letter) should be made to contact them as specified in protocol [Section 7.2.1](#).

Subjects who are withdrawn from the study for reasons other than safety, the decision to replace them by an equal number of newly enrolled subjects will be taken by the Sponsor.

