### **5.2 Prohibited treatment**

Any cardiac intravenous inotrope such as dobutamine or milrinone is prohibited. Digitalis is allowed if the patient has been on a stable dose for at least 2 weeks prior to entry into the study.

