### **6.3 Permitted dose adjustments and interruptions of study treatment**

Should there be any technical problems with the infusion line (i.e. infiltration, infusion pump malfunction) the infusion must be restarted within 30 minutes or the patient will be considered discontinued from treatment and the infusion shall not be restarted.

Dosage may be discontinued if required to address any safety concerns and should not be restarted. Dose adjustments of study treatment will not be permitted.

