#### **7.4 Study Stopping rules**

The study will be paused and no further dosing will be conducted pending a full, unblinded safety review if any of the following criteria are met:

- One or more SAE's are reported
- If 2 or more patients experience an AE that is similar and of severe grade
- If 2 or more patients have their infusion discontinued for safety or tolerability reasons
- A CLR325-treated patient develops anti-apelin antibodies
- The principal investigator and the sponsor consider that the number and/or severity of adverse events justify discontinuation of the study
- The sponsor unilaterally requests it

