## **9.2 Serious adverse event reporting**

### **9.2.1 Definition of SAE**

An SAE is defined as any adverse event (appearance of (or worsening of any pre-existing) undesirable sign(s), symptom(s) or medical conditions(s) which meets any one of the following criteria:

- is fatal or life-threatening
- results in persistent or significant disability/incapacity
- constitutes a congenital anomaly/birth defect
- requires inpatient hospitalization or prolongation of existing hospitalization, unless hospitalization is for:
  - routine treatment or monitoring of the studied indication, not associated with any deterioration in condition (e.g., worsening of heart failure symptoms)
  - elective or pre-planned treatment for a pre-existing condition that is unrelated to the indication under study and has not worsened since the start of study drug

- treatment on an emergency outpatient basis for an event not fulfilling any of the definitions of a SAE given above and not resulting in hospital admission
- social reasons and respite care in the absence of any deterioration in the patient's general condition
- is medically significant, i.e. defined as an event that jeopardizes the subject or may require medical or surgical intervention.

Life-threatening in the context of a SAE refers to a reaction in which the subject was at risk of death at the time of the reaction; it does not refer to a reaction that hypothetically might have caused death if more severe.

All malignant neoplasms will be assessed as serious under “medically significant” if other seriousness criteria are not met.

Any suspected transmission via a medicinal product of an infectious agent is also considered a serious adverse reaction.

Medical and scientific judgment should be exercised in deciding whether other situations should be considered serious reactions, such as important medical events that might not be immediately life threatening or result in death or hospitalization but might jeopardize the patient or might require intervention to prevent one of the other outcomes listed above. Examples of such events are intensive treatment in an emergency room or at home for allergic bronchospasm, blood dyscrasias or convulsions that do not result in hospitalization or development of dependency or abuse.

All AEs (serious and non-serious) are captured on the CRF, SAEs also require individual reporting to DS&E as per [Section 9.2.2](#).

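### Section 7.1 forces a stop for symptomatic hypotension only if treatment is persistent, so a brief intravenous inotrope or vasopressor course may not end the infusion

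*Protocol*

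**What the plan says.** Section 7.1 of the protocol lists circumstances in which study treatment must be discontinued. The one for low blood pressure reads "Occurrence of symptomatic hypotension requiring persistent medical intervention (i.e. fluid replacement or inotropic therapy"), followed by a clarification: "Note that change of patient position does not qualify as an intervention if the need for this change in position is not persistent". No duration, dose or number of repeats is given for fluids or drugs.

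Other provisions bear on the same event:

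- Section 5.2: "Any cardiac intravenous inotrope such as dobutamine or milrinone is prohibited". It does not say what happens to the study infusion if one is given.
- Section 7.1, deviations: treatment must end for "Any protocol deviation that results in a significant risk" to the subject's safety. The investigator must also stop if continuing is judged harmful on balance.
- Section 7.1, arrhythmia: a clinically significant arrhythmia ends treatment if it destabilizes the patient or needs medical treatment to terminate it. Persistence is not required.
- Section 6.3: "Dosage may be discontinued if required to address any safety concerns and should not be restarted".
- Section 7.4: one reported SAE means that "no further dosing will be conducted pending a full, unblinded safety review". Another trigger is "If 2 or more patients have their infusion discontinued for safety or tolerability reasons".
- Section 9.2.1: medically significant events are serious, including one that jeopardizes the subject "or may require medical or surgical intervention".

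**The concern.** Section 3.6 names a fall in blood pressure as a possible effect of CLR325, so the hypotension criterion covers a foreseen event. The rule is least clear when that event is treated with a vasoactive drug. If a site gives a short inotrope course, the pressure recovers and the site judges the need not persistent, the criterion does not clearly require it to end the infusion. CLR325, which is intended to raise contractility, could then run on beside a second inotrope. The Introduction associates existing intravenous inotropes with arrhythmia and mortality.

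Two sites could also act differently on the same event. Because 7.4 counts discontinued infusions, that difference can carry through to whether the study pauses. Section 10.4 provides for no data monitoring committee, so these written rules carry much of the study-level protection.

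**Working it through.** The plan gives no figure on this point, so the check is mainly a comparison of texts.

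**1. Two readings of the criterion.**

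- Reading A: the bracket defines the term, so fluid replacement or inotropic therapy of any length is the trigger.
- Reading B: the bracket names the kinds of intervention, and persistence is a further condition.

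The note on position change ties persistence to whether the need continues. That favours B as the natural reading. A remains possible.

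**2. Consistency with neighbouring rules.** The arrhythmia criterion in the same list has no persistence condition. Exclusion 16 in Section 4.2 bars a patient who had an inotrope infusion in the 24 hours before randomization, and 5.2 bans these drugs on study. Deliberate tolerance of an inotrope during the infusion would sit oddly with all three. Sections 6.8 and 6.9 do not settle it: the first gives no specific treatment advice for adverse events, and the second treats rescue medication as not applicable.

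**3. One case followed through.** Symptomatic hypotension occurs during the infusion, a short intravenous inotrope course is given, and the pressure recovers.

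| Provision | Leads to a stop or pause? | Condition |
|---|---|---|
| 7.1 hypotension | Reading A yes; Reading B no | Meaning of persistent |
| 7.1 deviation | Yes, if met | Significant risk must be judged present |
| 7.1 investigator judgment | Yes, if met | Continuing judged detrimental |
| 6.3 | Optional | Permissive wording |
| 7.4, SAE | Pauses further dosing | Event rated serious; a running infusion is not expressly addressed |

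For a vasopressor the position is weaker. The drug is not named in the bracket and not banned by 5.2, so its use is not in itself a deviation.

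**4. Effect on the 7.4 count.** Take two patients with this event.

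- Reading A: 1 + 1 = 2 discontinued infusions, which meets the threshold of 2, so the study pauses.
- Reading B: 0 + 0 = 0 if neither investigator stops on judgment, so this trigger is not met. If only one stops, the count is 1, still below 2.

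The contrast matters only if neither event is rated serious, the two do not meet the separate trigger for similar severe events, and neither the sponsor alone nor the sponsor with the principal investigator pauses the study for other reasons.

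**5. Cost of a stricter rule.** The maximum randomized is 40 (synopsis, both arms). The share of patients with a brief course that would otherwise not end the infusion is not in the documents; 1% to 5% is assumed. Extra stops: 40 × 0.01 = 0.4 and 40 × 0.05 = 2.0.

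**The case against.** The strongest reply is that the abbreviation in the bracket means *that is*, so inotropic therapy is itself the persistent intervention. On that view, the single exception for position change implies no exception for drugs. These drugs are also normally given as infusions, which are continuing treatments. This reading is fair but not compelled, because persistence remains attached to the intervention and the note explains it by continuing need.

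The second reply is that the safety net is wide, and most of it stands. Giving a banned drug is a deviation, the investigator must stop if continuing is harmful, and several arrhythmias and a confirmed fall in cardiac index have their own stops. Hypotension treated with an inotrope fits the medically significant limb of 9.2.1 closely, and one SAE pauses dosing. A reader might infer that the protocol allows CLR325 to continue beside an inotrope without protection. The documents do not support that: a stop would be likely in most cases. What remains is that each of these routes depends on a judgment or a classification.

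The third reply is that the words *medical intervention* are general enough to include vasopressors. That is arguable, but naming them costs nothing.

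A reader might also infer that, because 6.10 and 9.1 ask for dates and not clock times, events cannot be ordered against the infusion. That does not follow. The eCRF and Site Operations Manual are not shown and may hold time fields. Section 9.1 also records the action taken on study treatment, and hourly vital signs, telemetry and Holter add timing.

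**Conclusion.** The point holds as a minor one: a cheap improvement to a mandatory safety rule. On its natural reading, 7.1 does not make a brief, successful intravenous inotrope course for symptomatic hypotension a mandatory stop. That fits poorly with the ban in 5.2 and the arrhythmia criterion, and it leaves one 7.4 trigger open to interpretation (2 stops or possibly 0 for the same two patients).

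The conclusion rests on the protocol wording alone and on the event not being caught by a conditional provision. Its frequency cannot be estimated from the documents. A tempting further step is to say that the primary safety comparison is distorted. It is not: adverse events are tabulated by arm whether or not the infusion was stopped. Screening out transient events such as a brief change of position is a reasonable choice and is not criticized.

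**What to change.** (a) Section 7.1: replace the hypotension criterion with *Symptomatic hypotension treated with any intravenous inotrope or vasopressor, of any duration, or requiring persistent fluid replacement*. Keep the note on position change. Whether fluid replacement is persistent remains a matter of judgment, which is acceptable for a short fluid bolus.

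(b) Section 5.2: add *If an intravenous inotrope is needed to treat an adverse event, the study infusion is stopped and not restarted.* No end time needs to be added to the ban.

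Separately, confirm that the eCRF has time fields for adverse events and intravenous vasoactive drugs on Days 1 and 2. This is a check, not a required change.

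The cost is two short wording changes, with no extra visits or procedures. The downside is an occasional additional early infusion stop: 0.4 to 2 patients among at most 40 under the assumed 1% to 5%.

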## **Corporate Confidential Information**

The study will be comprised of a screening period of approximately 7 weeks (Day -45 to Day 1), a baseline period (Day 1), a treatment period (Day 1-2) and a follow up period (Days 3-28). Each treatment period will be comprised of a baseline pre-dosing interval (hour -1 to hour 0), an inpatient dosing interval (hour 1 to hour 18), and an inpatient post-dosing interval (hour 18 to hour 28). In addition, patients will have a follow-up visit (Day 10) and an end-of-study visit on Day 28.

On Day -45 to 1, screening evaluations will be performed. Study inclusion/exclusion criteria as well as medication use will be assessed during the screening and baseline periods. Patients who meet all of the inclusion and none of the exclusion criteria at screening will report to the study site on Day 1 of the baseline period, at a time specified by the investigator, and if they continue to meet all inclusion and none of the exclusion criteria, will remain in-house until the final 28 hour inpatient assessment in the treatment period.

[figure not shown]
On Day 1, pre-dose laboratory evaluations, cardiac hemodynamic monitoring, and 3-lead continuous telemetry monitoring will be performed. The sponsor will pre-specify if hemodynamics are to be monitored by a PA catheter, echocardiography, or both for each cohort. For PA catheter cohorts, cardiac hemodynamics will be monitored continuously using a pulmonary artery catheter (that will have been placed for standard of care clinical indications by the subject's caregiver prior to randomization in the study)

**Corporate Confidential Information** Intracardiac pressures (right atrial, pulmonary artery) will be recorded every hour during the treatment period. Cardiac outputs will be obtained at hours -1, 0, 1, 3, 6, 8, 10, 12, 18, 20, 24, and 28 of the treatment period. If not needed for standard of care clinical indications, the pulmonary artery catheter may be removed after the final cardiac output measurement at hour 28. For echocardiographic cohorts, echocardiograms will be obtained during the treatment period as specified in the SOM. Note that the sponsor's decision regarding obtaining the echocardiogram will be applied uniformly across all patients in the cohort.

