## 8 Procedures and assessments

**Table 8-1 Assessment Schedule**

Study Phase	Screening	Baseline	Treatment												Follow-up	EOS
Visit Numbers 	V1	V2	V3												V4	V777
Study Day(s) (windows)	-45 to 1	1	1 to 2												10 (-3 +3)	28 (-5 +5)
Time (post-dose)	-	-	-1h 	0h	1h	3h	6h	8h	10h	12h	18h	20h	24h	28h	-	-
Informed consent	X															
CCI		X														
Inclusion / Exclusion criteria	X	X														
Medical history/current medical conditions	X	X														
Concomitant therapies	X	X														
Demography	X															
Alcohol Test and Drug Screen	X															
Hepatitis 	X															
Pregnancy test	X	X 														
Body weight	X	X											X		X	X
Fluid Input and Output			X													
Vital Signs	X	X	X 												X	X
Physical examination	X	X											X 		X	X
Hematology	X	X					X			X	X		X		X	X
Blood chemistry	X	X					X			X	X		X		X	X
Coagulation	X	X								X			X		X	X
Urinalysis	X	X											X		X	X
28-hr urine collection			X 													

Study Phase	Screening	Baseline	Treatment												Follow-up	EOS	
Visit Numbers 	V1	V2	V3												V4	V777	
Study Day(s) (windows)	-45 to 1	1	1 to 2												10 (-3 +3)	28 (-5 +5)	
Time (post-dose)	-	-	-1h 	0h	1h	3h	6h	8h	10h	12h	18h	20h	24h	28h	-	-	
ECG evaluation	X	X		X 			X 			X 	X 		X 	X 	X	X	
CCI		X															
PK blood collection 	See table below																
CCI	See table below																
	See table below																
	See table below																
	See table below																
Immunogenicity		X													X	X	
Cardiac Hemodynamic monitoring 		X	X														
PA catheter derived Cardiac Output 			X														
Mixed venous blood gas 			X														
Telemetry cardiac monitoring 			X														
Echocardiogram 		X	X														
AICD Interrogation 		X														X	
Study drug administration				X													
Subjects domiciled			X														
Study completion information																X	
AEs and SAEs	X 																

 Visit structure given for internal programming purpose only

 (-) 1 hour assessments need to be at LEAST 1 hour prior to dose administration.

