## Corporate Confidential Information

### 8.3.2 Invasive hemodynamic monitoring

For PA catheter cohorts, the clinically indicated pulmonary artery catheter placed prior to entry into the study will remain in place until the end of the treatment period. The following parameters are measured:

- Right atrial pressure (RAP) in mmHg
- Systolic and diastolic right ventricular pressure (RVP) in mmHg – only required in patients with a PA catheter with RV ports capable of measuring RV pressures.
- Systolic and diastolic pulmonary arterial pressure (PAP) in mmHg
- Pulmonary capillary wedge pressure (PCWP) in mmHg
- Cardiac output (CO) in L/min
- Brachial systolic blood pressure (SBP), diastolic blood pressure (DBP), and heart rate - measured with each set of hemodynamic measurements

In addition pulse oximetry will be used to measure

- Peripheral arterial oxygen saturation SaO2 in %

Derived hemodynamic parameters are:

- Systemic vascular resistance (SVR) in dynes•sec/cm^5
- Pulmonary vascular resistance (PVR) in dynes•sec/cm^5
- Mean PAP in mmHg
- Stroke volume (SV) in mL
- Cardiac index (CI) in L/min/m^2

The hemodynamic measurements are repeated as indicated in the Site Operations Manual. In the event of any clinically significant change in hemodynamic measurements, additional hemodynamic measurements will be obtained at greater frequency as outlined in the Site Operations Manual. The hemodynamic measurements are done immediately before blood

collection at each time point. All hemodynamic parameters will be entered in the eCRF. Details of the hemodynamic measurements will be described in the Site Operations Manual.

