### **8.3.3 Echocardiogram**

A limited echocardiogram will be performed for an entire dosing cohort for those cohorts designated by the sponsor as echocardiography cohorts. If the site enrolls a subject in the echocardiographic cohort, the baseline scan will be evaluated locally to confirm patients with a lateral E/E' ratio of  $<7$  will be excluded.

The complete technical details of the equipment and machine settings will be captured in a separate echocardiographic manual prepared by an imaging CRO who will perform all analysis for determining cardiac output, ventricular volumes, and left ventricular ejection fraction. In brief, a Doppler flow evaluation to determine the blood flow velocity across the aortic valve will be acquired over multiple cardiac cycles which, along with heart rate, will be used to determine cardiac output. Additional measurements of ventricular volumes (systole and diastole) and left ventricular ejection fraction will also be captured. The image data will be collected from sites by an imaging CRO for central reading and reporting of the quantitative image analysis. A detailed Echocardiogram Manual will be provided to all sites participating in this imaging assessment which includes the acquisition and image transfer details.

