### **Corporate Confidential Information**

Holter data will be processed centrally and results will be sent electronically to Novartis (or designated CRO).

For echocardiograms, a dedicated imaging CRO will collect all echo data from the sites and send for quantitative analysis to a blinded expert reader. The analysis results will then be collected by the imaging CRO and transformed into a Novartis format defined by a data transfer specification. The transformed output will then be sent to Novartis data management for incorporation into the Clinical Study Report (CSR). The imaging CRO will be responsible for all image data clarification forms and missing data at all sites.

At the conclusion of the study, the occurrence of any emergency code breaks will be determined after return of all code break reports and unused drug supplies to Novartis.

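### Does the mandatory cardiac index stop in Section 7.1 need a cohort limit, when echo-only cohorts have no cardiac index described at the bedside?

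*Protocol*

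**What the plan says.** Protocol Section 7.1 lists the circumstances in which study treatment has to end. One is "A drop in cardiac index of > 30% as compared to the average of all cardiac index measurements obtained prior to" the start of infusion. A value showing such a fall must be repeated, and the drug is stopped only if the repeat confirms it. No cohort is named. Another bullet in the same list does carry a limit: "AICD discharge or anti-tachycardia pacing by the AICD in a patient with an AICD in place".

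Section 3.1 leaves the monitoring method to the sponsor: "The sponsor will pre-specify if hemodynamics are to be monitored by a PA catheter, echocardiography, or both for each cohort". Echo-only cohorts are therefore possible, and exclusion criteria 15 and 17 provide for echocardiographic cohorts.

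Cardiac index is listed in Section 8.3.2, which opens "For PA catheter cohorts, the clinically indicated pulmonary artery catheter placed prior to entry into the study will remain in place". The visible cardiac output row of Table 8-1 is labelled "PA catheter derived Cardiac Output". For echocardiography, Section 8.3.3 refers to a manual from "an imaging CRO who will perform all analysis for determining cardiac output, ventricular volumes, and left ventricular ejection fraction". The one local echo reading it describes concerns eligibility: "the baseline scan will be evaluated locally to confirm patients with a lateral" E/E' ratio below 7 are excluded. Section 10.3 routes the echo results through a blinded expert reader to sponsor data management for the study report.

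**The concern.** The bullet needs three values while the drug is running: a pre-infusion average, an on-infusion cardiac index, and a repeat. In an echo-only cohort the visible protocol describes no way for the investigator to have any of them. Echo cardiac output is worked out centrally, and no return to the site is mentioned. Read literally, a mandatory stop covers every patient but can be carried out only in some.

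Two things would be at stake. An investigator might not know whether the criterion applies in an echo-only cohort. And Section 7.4 pauses the study when two or more infusions are discontinued for safety or tolerability, so a criterion that works in some cohorts only could seem to give that count a different meaning from one cohort to the next.

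**Working it through.** No sample size, power or error rate enters here, so the check sets the passages side by side.

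1. **Is the bullet unqualified?** Yes. Section 7.1 names no cohort, whereas inclusion criterion 6, exclusion criterion 17 and Sections 8.3.2 and 8.3.4 all restrict themselves to PA catheter cohorts where that is meant.

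2. **What does the bullet act on?** On cardiac index values obtained before and during infusion. Where none is obtained, nothing can trigger it and nothing can be repeated. It does not itself order a measurement.

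3. **Where is cardiac index obtained?** In the visible text, only in Section 8.3.2. Section 8.3.3 gives cardiac output, ventricular volumes and ejection fraction as the echo outputs; cardiac index is not among them.

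4. **Does the rule fit the catheter schedule?** Section 3.1 gives 12 cardiac outputs:
   - hours -1 and 0, at or before the start: 2
   - hours 1, 3, 6, 8, 10 and 12, during infusion: 6
   - hours 18, 20, 24 and 28, at or after the end: 4
   - 2 + 6 + 4 = 12

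   The average, the trigger and the repeat all have a source there. The count says nothing about echo-only cohorts; it shows only which setting the bullet was written for.

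5. **Is other catheter text equally loose?** Yes. Section 5.4 attributes limited mobility to the PA catheter for all patients, and footnote 11 of Table 8-1 describes catheter monitoring with no cohort limit. Neither would be applied to a patient without a catheter. The Section 7.1 bullet fits the same drafting habit.

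6. **How many patients could be involved?** The synopsis caps randomization at 40. Section 3.1 makes the first cohort a PA catheter cohort of 6 + 2 = 8. If it is filled, at most 40 - 8 = 32 could be in echo-only cohorts. The actual number is not given and could be 0.

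7. **What still protects those patients?** In every cohort Section 7.1 keeps the stops for blood pressure, symptomatic hypotension, arrhythmia, ischemia and laboratory values, and the investigator's duty to stop when continuing would be detrimental. Table 8-1 keeps hourly vital signs, and Section 8.4.9 real-time telemetry.

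8. **Does Section 7.4 suffer?** Hardly. It counts infusions stopped for safety and does not compare cohorts. The review it starts is unblinded, and the sponsor, itself unblinded under Section 6.5, has chosen each cohort's monitoring method and so knows which cohorts had a catheter. A single SAE also pauses the study.

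**The case for a change.** The strongest contrary case is that a mandatory stop should show its scope in the protocol itself. Section 3.6 counts the stopping rules among the means of limiting risk, and Section 9.7 says the criteria for stopping study or treatment have already been set out in the protocol. Echo cohorts do produce a cardiac output, the quantity from which cardiac index is derived. An investigator might therefore think a local echo calculation is expected, or wait for a central result. For Holter data, Section 8.4.9 says plainly that results come too late for the site and adds telemetry; nothing comparable is said for echo.

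What stands is that the bullet is loosely worded. The conclusion that the investigator cannot tell what applies does not stand. Cardiac index is listed only for PA catheter cohorts, and the protocol asks no site to calculate it from an echo. The contrast with the AICD bullet is weak: having a device is a patient attribute, and mentioning it does not show that every measurement-dependent bullet was meant to carry a limit.

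The claim that no bedside value exists also cannot be proved from what is visible. Parts of Section 3.1, the block before Section 8.3.2 and footnote 12 of Table 8-1, which is attached to the cardiac output row, are blacked out. Echo timing is left to the Site Operations Manual and technical details to an echocardiographic manual, neither of which is shown. Section 10.3 describes a data-management route without excluding another.

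**Conclusion.** No change to the plan follows. This is a missing qualifier that the rest of the document supplies: the criterion operates where cardiac index is measured, which on the visible text means cohorts with a PA catheter, including those monitored by both methods. Naming the cohorts in the bullet would record that reading without altering a measurement, an analysis or a decision. The alternative, a bedside echo value feeding the rule, would need local readings that the visible plan does not describe. Whether that is wanted is a clinical choice for the sponsor, on which this review takes no position.

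The statistical size is nil: no estimate, test or probability in the protocol depends on it. In patients, the most it could touch is 32 of 40, with the true number unknown, and those patients keep every other stop in Section 7.1. The conclusion assumes that the blacked-out text and the manuals do not contradict the natural reading. If the protocol is edited for other reasons, Sections 7.1, 8.3.2, 8.3.3 and 10.3 can be aligned in wording at the same time; nothing here calls for an amendment of its own.
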